Statistical Analysis Plan

Compound Name:	TEW-7197
Protocol no:	MP-VAC-105(version 1.2)
IRB No:	18-0122
NCT Number	NCT03704675
Study Title:	A randomized, open, cross-over design clinical trial to investigate the safety, tolerability, and pharmacokinetics of TEW-7197 after a single oral administration of TEW-7197 200 mg under fed or fasting conditions in healthy male subjects

Statistical analysis	
• Demographic and baseline characteristics By TEW-7197 sequence, descriptive statistics (number of subjects, mean, standard deviation, range, minimum, median, maximum) were tabulated for demographic information such as age and sex and physical measurement/baseline characteristics such as height, weight, body mass index, drinking level and blood donation, and frequency and percentage were tabulated for categorical data. In order to confirm validity of randomization and subsequent analysis, statistical significance was assessed using an independent sample T test or Mann-Whitney test for continuous variables by sequence.• Pharmacokinetic analysis After calculating pharmacokinetic parameters by patient, descriptive statistics such as mean, standard deviation and CV% were presented by dose group. Descriptive statistics were presented for mean, standard deviation and CV% by treatment (fed/fasting), and the point estimate and 90% confidence interval of the mean difference between treatments were estimated by using log-transformed C_{max} and AUC_t.• Safety evaluation For adverse events and adverse drug reactions that occurred in this study, frequency (number of subjects), percentage and number of events were presented according to SOC and PT by dose group and treatment. Frequency (number of subjects), percentage and number of events were also presented for adverse events and adverse drug reactions according to SOC and PT by severity. Chi-square test or McNemar's test was used to evaluate a statistical significance between treatments. For vital signs, physical examination, 12-lead ECG, echocardiography and each item of clinical laboratory evaluations, descriptive statistics (number of subjects, mean
----------------------	--

	standard deviation, minimum, median, maximum and change from baseline (difference, change rate)) were tabulated by each measurement time, and for categorical data, frequency and percentage were tabulated. Concomitant medication was presented with lists.
--	---

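### Do the baseline significance tests between sequences put the randomisation or the fed/fasting comparison at risk?

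*Combined protocol and SAP*

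**What the plan says.** The SAP's Statistical analysis section first calls for baseline tables by sequence. They cover "demographic information such as age and sex and physical measurement/baseline characteristics such as height, weight, body mass index, drinking level and blood donation". It then adds a test and says what it is for: "In order to confirm validity of randomization and subsequent analysis, statistical significance was assessed using an independent sample T test or Mann-Whitney test". The test is limited to continuous variables: "independent sample T test or Mann-Whitney test for continuous variables by sequence". The stated purpose is to confirm that both the randomisation and the later analysis are valid.

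The section gives no significance level for these tests, no closed list of variables, no rule for choosing between the two tests, and no step to take if a result is significant.

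The title describes the study as "A randomized, open, cross-over design clinical trial to investigate the safety, tolerability, and pharmacokinetics of TEW-7197". The main comparison, under Pharmacokinetic analysis, is set out separately: "the point estimate and 90% confidence interval of the mean difference between treatments were estimated by using log-transformed C_{max} and AUC_t". That text does not mention the baseline tests or any baseline covariate. Under Safety evaluation, treatments are compared by a chi-square or McNemar's test, again without reference to baseline results.

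**The concern.** The tests are asked to do two things that they cannot do.

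- **Confirm the randomisation.** If sequences were allocated at random, the null hypothesis of no systematic difference holds by construction, and a small p-value is a chance event. A large p-value in a small study reflects low power as much as balance.
- **Confirm the later analysis.** Each subject is measured fed and fasting, so balance between sequences in age or weight is not what makes the comparison valid.

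Read literally, the sentence turns the baseline table into a validity check that sound trials will sometimes fail. What would be at stake is a report that wrongly doubts its own randomisation, or an analyst who alters the PK comparison because of a chance difference.

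**Working it through.** The SAP gives no error rate for this step, so there is no figure to reproduce. Two checks apply: how often a false alarm would occur, and whether one could reach the results.

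**1. Rate of false alarms**

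Inputs:
- Number of tests, k. Age, height, weight and BMI are clearly continuous, so k is at least 4. Drinking level and blood donation may be recorded as continuous, giving k = 5 or 6. Sex is categorical and all subjects are male. The list is open-ended, so 4 to 6 is an assumption.
- Significance level, α. Not stated; 0.05 two-sided is assumed, with 0.10 as a sensitivity case.

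If the variables were independent, P(at least one significant) = 1 − (1 − α)^k.

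| k | α = 0.05 | α = 0.10 |
|---|---|---|
| 4 | 1 − 0.95^4 = 18.5% | 1 − 0.90^4 = 34.4% |
| 5 | 1 − 0.95^5 = 22.6% | 1 − 0.90^5 = 41.0% |
| 6 | 1 − 0.95^6 = 26.5% | 1 − 0.90^6 = 46.9% |

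BMI is computed from height and weight, so independence overstates the rate. A simulation of t tests at 5% allowed for this, with 20,000 trials per setting. It assumed normal variables, a height–weight correlation of 0.3 or 0.5, and 6, 12 or 20 subjects per sequence, none of which the SAP states.

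| k | Range over the six settings |
|---|---|
| 4 | 15.9% to 16.2% |
| 5 | 19.9% to 20.6% |
| 6 | 23.5% to 24.5% |

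The number of subjects hardly matters, as expected when the null hypothesis is true. Taking both tables at 5%, the range is about 16% to 26%. This is the rate of seeing a p-value below 0.05. It is not the rate of declaring the trial invalid, because the SAP has no such decision.

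**2. Whether a false alarm can reach the results**

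Assume two sequences and two periods, and write the log PK value of subject i as

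y = μ + s_i + (period effect) + (food effect) + error,

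where s_i carries everything stable about the subject: age, height, weight, habits. Let π1 and π2 be the period effects and τ the fed minus fasting effect. The expected fed minus fasting difference within a subject is

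- fed first: τ + (π1 − π2)
- fasting first: τ − (π1 − π2)

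The term s_i has cancelled from both. The average of the two sequence means is τ, with the period effect removed as well. A difference between sequences in the average of s_i therefore does not enter the estimate, and its size is irrelevant to the interval.

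**3. With and without the tests**

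| Item | Tests kept | Tests deleted |
|---|---|---|
| Chance of at least one baseline p < 0.05 under sound randomisation | about 16% to 26% | none run |
| Fed/fasting estimate and 90% interval | as planned | identical |
| Safety comparisons | as planned | identical |
| Baseline descriptives by sequence | reported | reported |

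**The case for a change.** The strongest case for a change is that this is more than a habitual column of p-values. The SAP names a purpose, the purpose is mistaken, and the check has neither a defined trigger nor a defined consequence. That leaves room for improvised decisions, and removing the tests costs almost nothing. Whether allocation was carried out properly is better checked by comparing the randomisation list with the sequences actually given.

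The criticism of the rationale stands: these tests cannot confirm validity, and a plan written afresh would do better without them.

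The consequence does not follow. With no decision attached to a significant result, a wrong verdict on the randomisation is an inference from one clause of rationale. Changes to the PK comparison are a further conjecture, since the PK text names its outcomes and interval and provides for no adjustment. It would also go too far to call the p-values wholly uninformative. In an open trial a gross baseline difference could, weakly, point to an allocation error, because the null hypothesis is assured only if allocation was carried out as intended.

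**Conclusion.** No change follows, because there is nothing to gain in the results. The rationale is overstated, and a significant baseline difference would be seen in about 16% to 26% of soundly randomised trials, assuming four to six variables each tested at two-sided 5%. At an assumed 10% level with independent variables the figure would be 34% to 47%. In neither case does the plan link the p-values to the fed/fasting interval or to the safety comparisons, and the within-subject contrast removes stable baseline traits. That last step assumes a two-sequence, two-period layout with subject effects additive on the log scale. Deleting the tests would alter no estimate, interval, power, bias or safety finding. An analyst can report the table as description and treat an isolated small p-value as chance without any amendment.

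### Does a PK summary by dose group in a one-dose food-effect cross-over, with no geometric means named, mislead about the food effect?

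*Combined protocol and SAP*

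**What the plan says.** The study title describes "A randomized, open, cross-over design clinical trial" of safety, tolerability and pharmacokinetics "after a single oral administration of TEW-7197 200 mg under fed or fasting conditions in healthy male subjects". There is one dose level, and the factor being compared is the fed or fasting state.

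The Pharmacokinetic analysis part of the SAP then makes three statements:

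- After parameters are calculated for each participant, "descriptive statistics such as mean, standard deviation and CV% were presented by dose group".
- The next sentence begins "Descriptive statistics were presented for mean, standard deviation and CV% by treatment (fed/fasting" and so plans a summary for each condition.
- The same sentence goes on to the comparison: "the point estimate and 90% confidence interval of the mean difference between treatments were estimated by using log-transformed" Cmax and AUCt.

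The Safety evaluation part uses the same term for adverse events, which "were presented according to SOC and PT by dose group and treatment".

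The SAP does not define dose group, does not say that fed and fasting profiles are combined, and does not say whether the mean is arithmetic or geometric.

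**The concern.** Two features look wrong.

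First, grouping by dose makes no distinction when everyone receives 200 mg. Taken at face value, the table has one column holding both profiles from each completing subject. Its mean would describe neither condition, and its SD and CV% would mix the food effect with variation between subjects. Someone planning a later study might take that CV% as the variability of the drug.

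Second, an unqualified mean and SD are naturally read as arithmetic, while the inference is on the log scale and so leads to a ratio of geometric means. If variability differs between fed and fasting, a reader who divides the two tabulated means will get a food effect that differs from the analysed one.

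**Working it through.** The SAP states no CV, food effect or sample size for this point, so there is no planned figure to reproduce. From the documents come one dose level, a cross-over, a by-condition summary and log-scale inference with a 90% interval. All CVs and fed/fasting ratios below are assumptions.

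**1. What the pooled column would show, if it were produced.** Let the fasting mean be 1, the fed mean R, and the CV within each condition c. For an equal mixture of the two:

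- pooled mean = (1 + R)/2
- pooled variance = c²(1 + R²)/2 + (R − 1)²/4
- pooled CV = √(pooled variance) / pooled mean

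With c = 30%:

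| R | Pooled mean | Pooled variance | Pooled CV |
|---|---|---|---|
| 0.6 | 0.80 | 0.0612 + 0.0400 = 0.1012 | 39.8% |
| 0.8 | 0.90 | 0.0738 + 0.0100 = 0.0838 | 32.2% |
| 1.0 | 1.00 | 0.0900 + 0 = 0.0900 | 30.0% |
| 1.25 | 1.125 | 0.1153 + 0.0156 = 0.1309 | 32.2% |
| 1.5 | 1.25 | 0.1463 + 0.0625 = 0.2088 | 36.6% |
| 2.0 | 1.50 | 0.2250 + 0.2500 = 0.4750 | 45.9% |

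The inflation is nil without a food effect, small for a modest one and large for a doubling. In every row the separate fed and fasting columns still show 30%, because the SAP plans them as well.

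**2. Arithmetic against geometric ratio.** For log-normal data the arithmetic mean is the geometric mean times √(1 + CV²). Hence

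ratio of arithmetic means / ratio of geometric means = √[(1 + CV_fed²)/(1 + CV_fast²)].

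- 30% in both: √(1.09/1.09) = 1.000
- fasting 30%, fed 50%: √(1.25/1.09) = 1.071
- fasting 30%, fed 60%: √(1.36/1.09) = 1.117
- fasting 30%, fed 70%: √(1.49/1.09) = 1.169

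There is a gap only if the two CVs differ. The same relation lets a reader recover approximate geometric means from the planned table by dividing each mean by √(1 + CV²), because both the mean and the CV% are listed by condition.

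**3. Whether either point reaches the inference.** The point estimate and 90% confidence interval come from log-transformed Cmax and AUCt, compared between fed and fasting. A pooled column is not an input to that comparison, and neither is an arithmetic mean. The SAP does not plan to report a ratio of arithmetic means, so the disagreement in step 2 appears only if a reader calculates one.

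**The case for a change.** The best case for a change is that the SAP seems to treat dose group and treatment as different things. The PK part names them in consecutive sentences, and the safety part lists both as grouping factors. If dose group simply meant fed or fasting, the same PK table would be specified twice. On that reading a pooled table is planned. Further, the list of statistics for the fed/fasting table, unlike the first list, has no open-ended wording, so geometric summaries are not clearly covered. The edit would cost a few words.

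Much of this stands. The term is redundant or undefined here, and geometric mean and geometric CV% would sit more naturally beside a log-scale analysis. What does not stand is the step to harm. Pooling and double counting are inferred from an undefined term that may be wording left over from a multi-dose plan. With one dose, crossing dose group with treatment in the safety tables gives back treatment alone. Even if the pooled column were printed, it would appear beside correct fed and fasting columns. A later trial would be mis-sized only if its planner passed over those and chose the pooled figure.

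**Conclusion.** No change follows. The dose-group wording is at most a slip, and any analyst preparing the tables will see that 200 mg is the only dose and that fed and fasting are the groups to compare. Arithmetic mean, SD and CV% beside log-scale inference are not an error, and adding geometric rows is a reporting preference.

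Followed exactly as written, the SAP still gives separate fed and fasting summaries and an unaffected point estimate and 90% interval. The illustrated effects (a 30% CV shown as 32.2% to 45.9% for food effects of 1.25-fold to 2-fold, and a 7% to 17% gap between mean ratios when a fasting CV of 30% meets a fed CV of 50% to 70%) rest wholly on assumed values. They vanish when there is no food effect or when the CVs are equal, respectively. They concern a redundant column and a ratio that the SAP does not plan to report.

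### Is the fed/fasting comparison deficient because only log Cmax and log AUCt are given a 90% confidence interval, and tmax is not?

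*Combined protocol and SAP*

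**What the plan says.** The study title describes a randomized, open, cross-over trial of "pharmacokinetics of TEW-7197 after a single oral administration of TEW-7197 200 mg under fed or fasting conditions" in healthy male subjects.

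The Pharmacokinetic analysis paragraph of the SAP has three elements:

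- Individual parameters are derived and summarised: "After calculating pharmacokinetic parameters by patient, descriptive statistics such as mean, standard deviation and CV% were presented by dose group".
- The same kind of summary is given for each condition: "Descriptive statistics were presented for mean, standard deviation and CV% by treatment (fed/fasting").
- The contrast between conditions is estimated: "the point estimate and 90% confidence interval of the mean difference between treatments were estimated by using log-transformed C_{max} and AUC_t".

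The parameters covered by the first two elements are not listed. Other tests appear elsewhere in the same section, but they serve different purposes. Under Demographic and baseline characteristics, "statistical significance was assessed using an independent sample T test or Mann-Whitney test for continuous variables by sequence". Under Safety evaluation, "Chi-square test or McNemar's test was used to evaluate a statistical significance between treatments". Neither applies to a pharmacokinetic parameter.

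**The concern.** Food can act on an oral drug by delaying absorption. Cmax measures the height of the peak and AUCt the extent of exposure; neither measures when the peak occurs. If food only delayed absorption, both planned ratios would lie near 1, and a reader could conclude that food has no effect although the peak came later.

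A table of tmax by condition would show the shift as a difference of two means, but an interval could not be rebuilt from it. The standard error of a within-subject difference depends on the correlation between a subject's fed and fasting values, and mean, SD and CV% do not carry that correlation. If the two sequences differed in size, the raw difference of means would also absorb part of any period effect. For a trial whose contrast is fed against fasting, an interval for the change in timing might therefore seem to be missing.

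**Working it through.** The plan states no figure on this point to reproduce. The check has two parts: what the text supports, and how much could be missed.

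**1. What the text supports.** There is one interval statement. It has one confidence level (90%) and covers two parameters (Cmax and AUCt, both log-transformed). tmax is mentioned nowhere. The phrase about calculating parameters for each participant presupposes a list that is not in the available text. Whether tmax is tabulated, or compared in more detail elsewhere, can therefore be neither confirmed nor excluded. The title gives safety, tolerability and pharmacokinetics as the subject of study. No objective, endpoint or hypothesis about rate or delay of absorption is stated.

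**2. What the planned ratios would show.** The documents give no half-life, absorption rate, sampling times or sample size, so all inputs here are assumptions: a one-compartment oral model, half-life 3, 6 or 12 h, and fasting ka 0.8, 1.5 or 3.0 per h.

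Concentration is proportional to ka/(ka − ke) × (exp(−ke·t) − exp(−ka·t)), with ke = ln 2 / half-life. The peak is at tmax = ln(ka/ke)/(ka − ke). A lag L replaces t by t − L. It leaves the peak height unchanged, moves tmax by L, and shortens the integration window for AUC to T by L.

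| Fed condition | Cmax ratio | AUC0–24 ratio | AUC0–48 ratio | tmax shift (h) |
|---|---|---|---|---|
| 1 h lag, same ka | 1.000 | 0.978–0.999 | 0.996–1.000 | +1.00 |
| 2 h lag, same ka | 1.000 | 0.955–0.998 | 0.991–1.000 | +2.00 |
| 1 h lag, ka 0.4 per h | 0.585–0.885 | 0.927–0.994 | 0.985–1.000 | +2.07 to +5.31 |

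The first two rows are the case behind the worry: the lag is hidden from both ratios. They require a delay with no change at all in absorption rate. In the third row absorption is also slower, and Cmax falls by 11.5% to 41.5% (1 − 0.885 and 1 − 0.585). That change is in a parameter the plan already gives an interval.

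**3. What the descriptive table lacks.** With equal SDs, the standard error of the difference is √(1 − r) times its value at zero correlation. This is √0.5 = 0.71 at r = 0.5 and √0.2 = 0.45 at r = 0.8. If a 0.5 h period effect is assumed and 12 subjects are split 8/4, the raw difference of means is off by 0.5 × (8 − 4)/12 = 0.17 h. Both points are correct. They limit how precisely a tabulated shift could be read, but they do not affect the Cmax or AUCt contrasts.

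**4. What an added interval would give.** One candidate is a Hodges-Lehmann difference from period differences compared between sequences. Simulation with an assumed 17-point sampling schedule and the same 1 h lag in every subject put its 90% interval above zero in 42–89% of trials at n = 8 and 74–100% at n = 12. If the lag varies between subjects (log-scale SD 0.8, mean still 1 h), these fall to 30–59% and 56–88%. The gain depends entirely on quantities that the documents do not give.

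Nor would such an interval be exactly 90%. Without ties, the closest attainable Mann-Whitney level of at least 90% is 94.3% with 4 per sequence, 90.7% with 6 and 91.7% with 8. tmax takes only scheduled sampling times, so ties are expected. With no lag simulated at n = 12, the interval excluded zero in 1–5% of trials, against a nominal 10%.

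**The case for a change.** The strongest case for the concern is this. Fed against fasting is the contrast in the title, and timing is a recognised part of how food can act. The one interval statement covers two parameters that do not respond materially to a pure delay, and an interval for tmax cannot be recovered from mean, SD and CV%. Adding one would need only concentration data already collected and a single table row.

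Most of this stands as description. The reading of the text is accurate, the lag calculation is right for the model assumed, and the point about the unreported correlation is correct. An extra tmax estimate would do no harm.

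It does not show an error. The available text is silent on tmax in a summary that also omits the parameter list. Silence in such a summary, with two passages removed, is not evidence that the plan lacks the comparison. Even if it does, no stated aim goes unanswered and no planned estimate is biased. The Mann-Whitney test named in the plan lends little support, because it is there to compare baseline variables between sequences, not to estimate a treatment effect.

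**Conclusion.** The concern does not hold. The plan estimates the fed/fasting contrast for peak and extent of exposure, and describes the calculated parameters by condition. Followed as written, it gives sound conclusions for Cmax and AUCt. At most, a pure delay would be reported without an interval; if tmax is among the unlisted parameters, its shift would still be visible as a difference of means. Under the assumed model, a 1 h or 2 h lag with unchanged absorption rate is the case both ratios would miss (Cmax 1.000, AUC 0.955–1.000). A lag with slower absorption would appear in Cmax (0.585–0.885).

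These sizes rest on assumed half-lives, absorption rates and lags. The simulated detection rates also rest on assumed sampling times, sample sizes and variability. The conclusion does not depend on them: the available text states no aim about absorption delay and does not allow the absence of a tmax comparison to be established. Wanting an interval for one more secondary parameter is a preference, not a fault in the plan.

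### Does the food-effect estimate need its cross-over model and its back-transformation spelled out?

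*Combined protocol and SAP*

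**What the plan says.** The Study Title describes "A randomized, open, cross-over design clinical trial" of one 200 mg oral dose, given fed or fasting to healthy men.

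Under Statistical analysis, the Pharmacokinetic analysis paragraph asks for the mean, standard deviation and CV% under each feeding condition. Its only inferential statement follows: "the point estimate and 90% confidence interval of the mean difference between treatments were estimated by using log-transformed" Cmax and AUCt. The paragraph names no model, no period, sequence or subject term, no treatment of subjects with data from one period only, and no conversion of the log difference to a ratio.

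Sequence appears in the Demographic and baseline characteristics paragraph, which begins "By TEW-7197 sequence, descriptive statistics" and adds that "statistical significance was assessed using an independent sample T test or Mann-Whitney test for continuous variables by sequence". The Safety evaluation paragraph allows either a chi-square test or McNemar's test between treatments. The SAP gives no sample size, variance, drop-out rate or equivalence limits.

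**The concern.** Each subject is measured in two periods, in a randomised order. Read literally, a mean difference on the log scale could be computed in three ways: as the treatment contrast from a model with period and subject, as a plain mean of within-subject differences, or as a difference between two unpaired means.

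The second puts any period effect into the residual and is biased if the sequences finish with unequal numbers. The third also discards the within-subject precision for which a cross-over is chosen. A result left on the log scale is not in the form a reader wants, which is a fed/fasting ratio. Since this is the only inferential comparison of exposure in the plan, a poor choice would affect the main pharmacokinetic result.

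**Working it through.** The plan states no figure that can be reproduced, so the check asks how much the three readings could differ.

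**Inputs.** From the SAP: two treatments, a cross-over, log scale, 90% interval. Assumed, because the SAP gives none: N = 12 to 24 subjects, within-subject CV 20% to 30%, between-subject CV 30% to 50%, and a log period effect π of 0 to 0.3. A π of 0.1, 0.2 or 0.3 means that exposure differs between periods by a factor of 1.11, 1.22 or 1.35.

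**Formulas.** Let σw² = ln(1 + CVw²) and σb² = ln(1 + CVb²). A subject's fed-minus-fasting log difference has mean τ − π in one sequence and τ + π in the other. With equal sequences the half-widths of the 90% interval are:

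- cross-over model: t(0.95, N−2) × √(2σw²/N)
- paired, no period term: t(0.95, N−1) × √((2σw² + π²N/(N−1))/N)
- unpaired: t(0.95, 2N−2) × √(2(σb² + σw²)/N)

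**Worked case** (N = 12, CVw 20%, CVb 30%, π = 0.2). σw² = ln 1.04 = 0.0392 and σb² = ln 1.09 = 0.0862.

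- Model: 1.812 × √(0.0784/12) = 0.147
- Paired: 1.796 × √((0.0784 + 0.0436)/12) = 0.181, ratio to the model 1.24
- Unpaired: 1.717 × √(0.2508/12) = 0.248, ratio to the model 1.69

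**Over the assumed ranges**, half-width relative to the cross-over model:

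| Reading | π = 0 | π = 0.1 | π = 0.2 | π = 0.3 |
|---|---|---|---|---|
| Paired, no period term | 0.99–1.00 | 1.02–1.06 | 1.11–1.24 | 1.24–1.49 |
| Unpaired (does not depend on π) | 1.34–2.53 | 1.34–2.53 | 1.34–2.53 | 1.34–2.53 |

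**Bias.** The plain paired mean is off by π(n2 − n1)/(n1 + n2), which is zero with equal sequences. With 12 and 8 completers and π = 0.2 it is 0.2 × (−4/20) = −0.04, a factor of exp(−0.04) = 0.961 on the ratio. In 20,000 simulated trials of that case (CVw 30%, true difference 0), the mean estimate was −0.041 for the plain mean and −0.001 for the model. Coverage was 90.4% and 90.0%, and the mean half-width 0.176 and 0.162.

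**Sequence term.** With complete data, sequence is a between-subject contrast. Once subject and period are in the model it does not move the fed-minus-fasting estimate, so its absence causes neither bias nor loss of precision.

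**Scale.** The mean of ln(fed) minus the mean of ln(fasting) is the log of the ratio of geometric means. Exponentiating the estimate and both limits gives the ratio and its 90% interval, with no further assumption and no change in inference.

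**The case for a change.** The best case for a change is that the SAP names its tests where it means them: a t or Mann-Whitney test at baseline, chi-square or McNemar's test for adverse events. It names none for the comparison that matters most. It also allows chi-square between treatments in the same cross-over, a test that treats fed and fasting observations as independent, so an unpaired reading of the pharmacokinetic sentence is not far-fetched. One more sentence in the plan would need no new data and would cost one residual degree of freedom.

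Part of this stands. The text permits a standard cross-over model without requiring one, and naming it would have been tidier. But silence is not a choice of the wrong method. The sentence never says that the difference is plain, unadjusted or unpaired. Log transformation, a 90% interval and a two-treatment contrast are the usual ingredients of a cross-over ANOVA or mixed model. The design is declared a cross-over in the title, sequence is tracked, and a paired test is among those listed for safety. The allowance for chi-square concerns adverse-event counts and does not govern the exposure comparison.

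**Conclusion.** No change is needed. This is a gap in detail that pharmacokinetic analysts fill as a matter of routine, with period, treatment and subject in the model and the result exponentiated to a fed/fasting ratio. No stated rule gives a wrong answer, and the SAP sets no equivalence limit or decision rule that a somewhat wider interval could be shown to cross.

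The penalty for the plainer paired reading is nil without a period effect and 2% to 6% in interval width at a log effect of 0.1. It becomes material only if exposure shifts between periods by about 20% or more, which nothing in the document suggests. Bias of about 4% on the ratio takes a log period effect of 0.2 together with a 12 to 8 imbalance in completers. The large figure, an interval up to 2.5 times as wide, depends on analysing a cross-over as two independent groups. That would cost precision, but with complete data it would leave the point estimate unchanged.

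All these sizes rest on assumed sample sizes, CVs and period effects. The conclusion would differ if the plan had prescribed an unpaired or unadjusted comparison, and it does not.

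### For fed versus fasting adverse events in a cross-over, the plan permits a chi-square test, which treats the same subjects as two independent groups

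*Combined protocol and SAP*

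**What the plan says.** The SAP's Study Title describes "A randomized, open, cross-over design clinical trial to investigate the safety, tolerability, and pharmacokinetics of TEW-7197", and the comparison is of a single dose of "TEW-7197 200 mg under fed or fasting conditions in healthy male subjects". The Pharmacokinetic analysis paragraph shows what treatment means in this plan: its summaries are given "by treatment (fed/fasting"). Treatment is therefore a factor that varies within a subject.

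Under Safety evaluation, adverse events and adverse drug reactions are tabulated so that "frequency (number of subjects), percentage and number of events were presented according to SOC and PT by dose group and treatment". The significance test for these is then given as "Chi-square test or McNemar's test was used to evaluate a statistical significance between treatments". No condition says when either test applies, and McNemar's form (exact, mid-p or large-sample) is not stated.

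Under Demographic and baseline characteristics, "statistical significance was assessed using an independent sample T test or Mann-Whitney test for continuous variables by sequence". The two sequences contain different people, so independent-sample tests are suitable there.

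**The concern.** An ordinary chi-square test on fed and fasting totals assumes that the two sets of records come from different people. In this design they come from the same people. The test sees only the two totals, and not how many subjects had an event in both periods, in one, or in neither. Its standard error is therefore wrong unless the within-subject correlation happens to be zero.

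Two things are at stake. The first is validity: the real error rate depends on a correlation that the plan does not give. The test is conservative if that correlation is positive and liberal if it is negative. The second is an open choice: with both tests permitted and no rule, the choice can be made after the data are seen, and a reader cannot tell which test lies behind a reported p-value. The title lists safety and tolerability among the aims, and this is the only significance test the plan names for adverse events.

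**Working it through.** The plan gives no figure to reproduce here: no sample size, alpha or event rate is stated for this comparison. Everything below is illustration under stated assumptions.

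**Assumptions (not from the plan).** N = 12, 16, 20 or 24 subjects with both periods; event risk p of 20%, 30% or 40% per period; two-sided 5%; within-subject correlation ρ. Chi-square means the uncorrected Pearson test on N fed and N fasting records.

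**1. Why the correlation matters.** With equal risk p in both periods, the difference in proportions has variance 2p(1−p)(1−ρ)/N. Chi-square uses 2p(1−p)/N. In large samples its true size is therefore P(|Z| > 1.96/√(1−ρ)):

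- ρ = −0.2: 1.96/√1.2 = 1.79, size 7.4%
- ρ = 0: size 5.0%
- ρ = 0.3: 1.96/√0.7 = 2.34, size 1.9%
- ρ = 0.6: 1.96/√0.4 = 3.10, size 0.2%

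**2. Small-sample type I error.** All paired tables were enumerated with multinomial weights, taking P(event in both periods) = p₁p₂ + ρ√(p₁(1−p₁)p₂(1−p₂)). The ranges are over the N and p grid.

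| ρ | Chi-square | Large-sample McNemar | Mid-p McNemar | Exact McNemar |
|---|---|---|---|---|
| 0 | 3.9-5.9% | 4.2-5.2% | 1.6-4.3% | 0.4-2.4% |
| 0.3 | 1.4-2.5% | 2.6-5.0% | 0.6-3.9% | 0.1-1.9% |
| 0.6 | 0.2-0.4% | 0.6-4.8% | 0.1-2.2% | 0.01-0.7% |

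**3. Same totals, different conclusions (N = 24).** Write b/c for the numbers of subjects with an event in one period only.

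*9 versus 3 subjects.* The difference is 6/24 = 0.25 and the pooled risk is 12/48 = 0.25. The standard error is √(0.25 × 0.75 × 2/24) = 0.125, so z = 2.0 and chi-square p = 0.046 whatever the pairing.

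*10 versus 4 subjects.* The pooled risk is 14/48 = 0.292 and the standard error is 0.131, so z = 1.905 and chi-square p = 0.057 whatever the pairing.

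In both cases b − c = 6. Large-sample McNemar takes (b−c)²/(b+c) as chi-square on 1 degree of freedom, and exact McNemar is a two-sided binomial test with probability ½.

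| b/c | Large-sample McNemar p | Exact McNemar p |
|---|---|---|
| 6/0 | 36/6 = 6.0, p = 0.014 | 0.031 |
| 7/1 | 36/8 = 4.5, p = 0.034 | 0.070 |
| 8/2 | 36/10 = 3.6, p = 0.058 | 0.109 |
| 9/3 | 36/12 = 3.0, p = 0.083 | 0.146 |
| 10/4 (only for 10 versus 4) | 36/14 = 2.57, p = 0.109 | 0.180 |

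Comparing large-sample tests with each other, the conclusion changes in both directions. For 9 versus 3 with 8/2 discordant, chi-square gives 0.046 and McNemar 0.058. For 10 versus 4 with 6/0 discordant, chi-square gives 0.057 and McNemar 0.014.

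**4. Power, true risks 20% versus 50%, ρ = 0.3.**

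| N | Chi-square | Large-sample McNemar | Mid-p McNemar | Exact McNemar |
|---|---|---|---|---|
| 12 | 33% | 42% | 28% | 14% |
| 16 | 44% | 55% | 47% | 32% |
| 20 | 53% | 64% | 61% | 48% |
| 24 | 63% | 73% | 72% | 61% |

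McNemar's test is not always the more powerful. At ρ = 0 and N = 24, chi-square has 61% power against 56% for mid-p and 46% for exact. The argument for McNemar's test is validity with paired data.

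**The case against.** **McNemar's test is already named.** This stands. The plan leaves a choice unresolved; it does not prescribe the invalid test, and nothing shows that chi-square was used. Even so, a named option that is invalid for this comparison is more than a missing detail.

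**Chi-square may be meant for independent groups, since the tables are also split by dose group.** This does not hold. The title gives one dose, and the sentence refers to comparison between treatments. Nor can chi-square mean McNemar's own chi-square statistic, because the plan offers the two as alternatives.

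**Setting large-sample chi-square against exact McNemar mixes two effects.** This stands as a caution. At 9 versus 3 with 7/1 discordant, exact McNemar gives 0.070 but large-sample McNemar gives 0.034, the same side of 5% as chi-square. The extreme pairings 9/3 and 10/4 also imply observed correlations of about −0.29 and −0.38. The changes of conclusion nevertheless survive between large-sample tests, in both directions.

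**The practical effect is limited.** Largely accepted. At zero correlation chi-square is close to nominal, and with positive correlation it is conservative. Inflation needs negative correlation, for which there is no particular reason. The adverse event counts and percentages, and the pharmacokinetic confidence intervals, do not depend on this test.

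**Conclusion.** The concern holds: the sentence is wrong as written, because one of its two tests assumes independence that a cross-over comparison of fed with fasting does not have. The plan does not allow the effect to be calculated. Under the assumed 12 to 24 subjects and 20-40% risk, a nominal 5% chi-square test runs at between about 0.2% and 5.9% for correlations from 0 to 0.6, and at 7.4% in large samples at −0.2. If correlation is positive, the main risk is missing a real difference in tolerability, not a false claim of one. A borderline result could also change sides depending on which permitted test is reported. The finding is confined to the safety comparison.

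**What to change.** Delete the chi-square option for fed versus fasting and fix the form of McNemar's test in advance. For example: *The proportion of subjects with at least one adverse event will be compared between fed and fasting by the exact McNemar test, in subjects with data from both periods.* The sentence should name one form throughout, or give a numerical threshold for switching, so that the choice is not reopened. It should also say whether testing is of any adverse event only or by SOC and PT as well; the plan does not say, and the example covers only the former.

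If less conservatism is wanted, the mid-p form can be named instead. Its type I error stayed at or below 4.3% in the grid for correlations 0 to 0.6, and reached 4.6% at −0.2.

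The cost is one sentence of SAP wording, plus a re-run on existing adverse event data if chi-square was used. There are two drawbacks. Subjects with only one period leave the test, though they stay in the tables. The exact form cannot reach p < 0.05 with fewer than six discordant subjects: 5 versus 0 gives 2 × (1/2)⁵ = 0.0625, and 6 versus 0 gives 2 × (1/2)⁶ = 0.031.
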